6.6.3. Efficacy Variable Definitions

Baseline Hormone Control

Severe: Baseline ACTH > 4x ULN and A4 > 2x ULN

Moderate: Baseline ACTH > 2x ULN and A4 > 2x ULN

Severe/Moderate: Baseline ACTH > 2x ULN and A4 > 2x ULN

Mild: Baseline ACTH \leq 2x ULN and A4 \leq 2x ULN

Hormone Control Responder

Week 12 ACTH < ULN and A4 < ULN

Hydrocortisone equivalents

Hydrocortisone equivalent (mg) = Corticosteroid (mg) × Conversion Factor, using the following corticosteroid dosages equivalence table (reference is hydrocortisone 20 mg):

Medication	Equivalent Dose	Conversion Factor
Cortisone Acetate	25 mg	0.8
Hydrocortisone	20 mg	1
Prednisone/Prednisolone/ Methylprednisolone	4 mg	5
Dexamethasone	0.25 mg	80
Betamethasone	0.6 mg	33.33

For example, if a subject receives 10 mg of prednisone, that is equivalent to 50 mg of hydrocortisone.

Upper limit of Normal (ULN)

The following are the upper limit of normal or targets based on the lab reference ranges.

Hormone	SEX	ULN/Target
Serum 17-OHP	males	< 1200 ng/dL
Serum 17-OHP	females	< 1200 ng/dL
ACTH	males	< 63.3 pg/mL
ACTH	females	< 63.3 pg/mL
A4	males	< 152 ng/dL
A4	females	< 262 ng/dL

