6.3. Data Presentation Conventions

Table, Figure and Listing titles

Table, figures and listing titles are denoted in underlined text in this SAP. For a complete list, see Appendix Section 11.3.

Reporting Formats

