6.4.5. Examination of Subgroups

The following subgroups are pre-defined:

1. Sex: [a] male, [b] female
2. Baseline hormone control: [a] severe/moderate control issues, [b] mild control issues
3. Baseline Glucocorticoid category: [a] Non-Dexamethasone [b] Dexamethasone

Selected analysis will be conducted using the subgroup analysis sets.

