9.5. Analysis of Secondary Efficacy Endpoints

Analysis of hormone data will be conducted only on subgroups.

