9.5.1. Efficacy Analysis of Hormones

Hormones [17-OHP; ACTH; A4; Testosterone] will be summarized using geometric means and geometric means ratios to assess change and percentage change.

A summary of [17-OHP; ACTH; A4; Testosterone] by Visit will include the observed parameter (using GM reporting format).

Figures

A serial figure with week as the x-axis and % change as the y-axis will be provided.

Separate serial figures will be provided for each hormone.

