9.5.2. Efficacy Analysis of Hormones by Subgroups

To characterize the consistency of the treatment effect for the primary endpoint, each hormone will be summarized using a combination of subgroups

A summary of [17-OHP; ACH; A4; Testosterone] by Visit: [subgroup] will be provided. The following subgroups will be summarized in separate summaries:

- Non-Dexamethasone subjects
- Non-Dexamethasone subjects with severe/moderate control issues
- Non-Dexamethasone subjects with mild control issues

Figures

A serial figure with week as the x-axis and % change as the y-axis will be provided.

Separate serial figures will be provided for each hormone.

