11.3. Tables, Figures and Listings

This index may be updated post finalization of the SAP.

Tables

Number	Title	Analysis Set
14.1.1.1.1	Enrollment by Investigator	Randomized
14.1.1.3	Analysis Sets	Randomized
14.1.1.4	Subject Disposition	Randomized
14.1.1.5.1	Summary of Protocol Deviation Identified Prior To Database Lock by Site	Randomized
14.1.1.5.2	Summary of Protocol Deviation Identified Prior To Database Lock by Treatment Group	Randomized
14.1.1.6	I/E Table	Randomized
14.1.2.1.1	Demographic and Baseline Characteristics	Safety
14.1.2.2.1	Summary of Baseline Hormones	Safety
14.1.2.3.1	Mini International Neuropsychiatric Interview	Safety
14.1.3.1	Medical History by System Organ Class and Preferred Term	Safety
14.1.3.2	Prior Medications	Safety
14.1.3.3	Prior Glucocorticoid Therapy	Safety
14.2.1.1	Summary of 17-OHP by Visit: Dexamethasone Subjects	Safety
14.2.1.2	Summary of 17-OHP by Visit: Non-Dexamethasone Severe/moderate Control Issues	Safety
14.2.1.3	Summary of 17-OHP by Visit: Non-Dexamethasone Severe/moderate Control Issues- LOCF	Safety
14.2.1.4	Summary of 17-OHP by Visit: Non-Dexamethasone Mild Control Issues	Safety
14.2.2.1	Summary of ACTH by Visit: Dexamethasone Subjects	Safety
14.2.2.2	Summary of ACTH by Visit: Non-Dexamethasone Severe/moderate Control Issues	Safety
14.2.2.3	Summary of ACTH by Visit: Non-Dexamethasone Severe/moderate Control Issues- LOCF	Safety
14.2.2.4	Summary of ACTH by Visit: Non-Dexamethasone Mild Control Issues	Safety
14.2.3.1	Summary of Androstenedione by Visit: Dexamethasone Subjects	Safety
14.2.3.2	Summary of Androstenedione by Visit: Non-Dexamethasone Severe/moderate Control Issues	Safety
14.2.3.3	Summary of Androstenedione by Visit: Non-Dexamethasone Severe/moderate Control Issues- LOCF	Safety
14.2.3.4	Summary of Androstenedione by Visit: Non-Dexamethasone Mild Control Issues	Safety
14.2.4.1	Summary of Testosterone by Visit	Safety
14.2.4.2	Summary of Testosterone by Visit: Males	Safety
14.2.4.3	Summary of Testosterone by Visit: Females	Safety
14.2.5	Summary of SF-36 by Visit	Safety
14.2.6	Summary of CAH Signs and Symptoms	Safety
14.2.7	Summary of Patient Global Impression of Change	Safety
14.2.8	Changes in Lipid Profile Summary by Visit	Safety

Number	Title	Analysis Set
14.2.9	Changes in Insulin Profile Summary by Visit	Safety
14.2.10	Changes in Body weight Summary by Visit	Safety
14.2.11	Summary of the Magnitude of Bothersome Symptoms	Safety
14.3.1.1	Study Drug Exposure	Safety
14.3.1.2	Study Drug Compliance	Safety

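### Subjects with only one of ACTH and A4 above 2x ULN have no control class, and the SAP output index then leaves the non-dexamethasone ones out of every by-visit summary of 17-OHP, ACTH and A4

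*SAP*

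**What the plan says.** **Classes.** SAP 6.6.3 sets "Severe/Moderate: Baseline ACTH > 2x ULN and A4 > 2x ULN". The entry that begins "Mild: Baseline ACTH" requires both hormones to be at or below 2x ULN. The separate Severe and Moderate entries also need both hormones raised. SAP 6.4.5 pre-defines two levels only: "Baseline hormone control: [a] severe/moderate control issues, [b] mild control issues".

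**Analysis text.** SAP 9.5 states: "Analysis of hormone data will be conducted only on subgroups". SAP 9.5.1 then says, without naming a subgroup: "Hormones [17-OHP; ACTH; A4; Testosterone] will be summarized using geometric means and geometric means ratios to assess change and percentage change". SAP 9.5.2 adds "The following subgroups will be summarized in separate summaries" and lists three groups: all non-dexamethasone subjects, those with severe/moderate control issues, and those with mild control issues.

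**Index.** For each of 17-OHP, ACTH and A4, SAP 11.3 lists four by-visit tables and four figures: dexamethasone, non-dexamethasone severe/moderate, the LOCF version of that, and non-dexamethasone mild. Testosterone has all-subject, male and female outputs. SAP 6.3 says of the outputs "For a complete list, see Appendix Section 11.3", while 11.3 says "This index may be updated post finalization of the SAP".

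**Protocol.** Section 9.3.1 asks for summaries that pool all subjects in each analysis population. Section 9.3.9 promises summaries of the endpoints by sex and by naïve or experienced status.

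**The concern.** The two control classes do not cover all subjects, and the indexed outputs for three hormones are built on them. A gap in a subgroup definition normally costs little, because the subject still counts in the overall analysis. Here no overall analysis of 17-OHP, ACTH or A4 is indexed, so the gap becomes an exclusion that depends on the subject's baseline hormone pattern.

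Hormone change is the only secondary objective of the study, and the null hypothesis in SAP 9.2 is stated for each hormone without any subgroup. If the index governs, no table for these three hormones matches that hypothesis. In an open-label study that allows data cuts (SAP 5.1.3) and an index that can change after the SAP is final, the handling of unclassified subjects could be settled after their results are known.

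**Working it through.** The plan gives no figure on this point, so there is none to reproduce. The check applies the rules and counts the outputs.

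**1. Which subjects have a class (SAP 6.6.3)**

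| ACTH | A4 | Class |
|---|---|---|
| > 2x ULN | > 2x ULN | Severe/Moderate |
| ≤ 2x ULN | ≤ 2x ULN | Mild |
| > 2x ULN | ≤ 2x ULN | none |
| ≤ 2x ULN | > 2x ULN | none |

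With the limits in 6.6.3, 2x ULN is 2 × 63.3 = 126.6 pg/mL for ACTH. For A4 it is 2 × 152 = 304 ng/dL in males and 2 × 262 = 524 ng/dL in females. No eligibility criterion uses ACTH or A4. The hormone entry criterion is 17-OHP of at least 800 ng/dL (Protocol 5.1.1 and 5.2.1), so nothing in the protocol rules out discordance.

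**2. Which indexed outputs contain a discordant subject (SAP 11.3)**

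- Tables 14.2.1.1–4, 14.2.2.1–4 and 14.2.3.1–4: 3 × 4 = 12.
- Figures 15.2.1.1–4, 15.2.2.1–4 and 15.2.3.1, .2, .5, .6: 3 × 4 = 12.
- All-subject or all-non-dexamethasone among them: 0 of 12 tables and 0 of 12 figures.
- A discordant non-dexamethasone subject is in 0 of the 24 outputs.
- A discordant dexamethasone subject is in the dexamethasone table and figure, so is not lost.
- Testosterone (14.2.4.1–3 and 15.2.4.1–3): 1 of 3 tables and 1 of 3 figures are all-subject.

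Discordant non-dexamethasone subjects remain in the baseline hormone table (SAP 7.8, 14.1.2.2.1), the listings (16.2.4.2.7, 16.2.6.1) and the testosterone outputs. None of these is an on-treatment summary of the other three hormones.

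**3. Text against index**

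| Summary of 17-OHP, ACTH, A4 | SAP text | Index |
|---|---|---|
| No subgroup | 9.5.1 describes it; 9.5 appears to bar it | absent |
| All non-dexamethasone | named in 9.5.2 | absent |
| Dexamethasone | not in 9.5.2 | present |
| Non-dexamethasone, by control class | named in 9.5.2 | present |

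The all-subject testosterone table also does not fit the restriction in 9.5.

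**4. Size**

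The final sample is 11 (SAP 4.3). One subject is 1/11 = 9.1%.

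The number of discordant subjects is not given. As an assumption only, take 6 to 11 non-dexamethasone subjects and a discordance rate of 10% to 50%. The expected number lost is then 6 × 0.1 = 0.6 up to 11 × 0.5 = 5.5. The chance of losing at least one is 1 − 0.9^6 = 47% up to 1 − 0.5^11, which is over 99%.

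**5. Cost of having no pooled summary**

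This cost arises even if no subject is discordant. The index splits 11 subjects into at most three disjoint groups. Three groups of at least 4 would need 12 subjects, so one group has 3 or fewer. The half-width of a 95% CI for the log geometric mean ratio, in SD units, is t(0.975, n−1)/√n:

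- n = 11: 2.228/3.317 = 0.672
- n = 4: 3.182/2 = 1.591, which is 2.4 times as wide
- n = 3: 4.303/1.732 = 2.484, which is 3.7 times as wide

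These ratios are on the log scale and assume the same SD in each set.

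**The case against.** The strongest reply is that the body of the SAP already keeps these subjects. Section 9.5.1 names no subgroup, and the first group in 9.5.2 is all non-dexamethasone subjects, so the loss arises only if an appendix that may be updated overrides the text. That is right, and it is why the conclusion is conditional on the index. It does not settle the matter: 6.3 refers to the index as complete, 9.5 supports its restriction to subgroups, and nothing says which governs.

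It can also be said that no affected subject has been shown. The SAP was written knowing the final sample size and some baseline data (4.3, 5.1.1), so the two classes may cover everyone. This stands: the true loss may be zero, and the range in step 4 rests on assumed rates. The missing pooled summary does not depend on it.

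The interval ratios describe subgrouping at n = 11, not the loss of discordant subjects. They hold on the log scale only, and a pooled SD 1.5 to 2 times larger would cut 3.70 to 2.47 or 1.85. This also stands, and they are used here only for the missing pooled summary.

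Finally, SAP 2 promises that substantive changes will be identified in the study report, and SAP 5.1.2 was not available for review. A departure recorded there cannot be excluded; 5.1.1 does not record one.

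**Conclusion.** The concern holds as stated. SAP 6.6.3 gives no class to a subject with exactly one of ACTH and A4 above 2x ULN. If the 11.3 index is followed, every such subject not on dexamethasone is missing from all on-treatment summaries of 17-OHP, ACTH and A4. Independently of that, three of the four secondary hormones have no indexed summary that pools all subjects, as Protocol 9.3.1 requires, and none by sex or prior exposure, as 9.3.9 requires.

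The consequence is moderate. The analysis is secondary and hypothesis-generating (SAP 9.4), the primary safety analysis is untouched, and all values are listed. A listing, however, gives no estimate of effect. This should be fixed before the analysis is run.

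**What to change.** 1. Remove the restriction to subgroups from SAP 9.5. Index all-subject by-visit tables and figures for 17-OHP, ACTH and A4, giving the geometric mean ratio to baseline with its 95% CI. Keep the subgroup outputs as supportive.
2. Index the all-non-dexamethasone summary that 9.5.2 already names, and add dexamethasone subjects to 9.5.2. These two groups cover everyone, so this step alone puts each subject in at least one by-visit summary per hormone.
3. State before the analysis how subjects with one hormone above 2x ULN are handled, for example as a separate category reported by listing if it is small.
4. Record in SAP 5.1.1 any departure from Protocol 9.3.1 that remains.

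The cost is SAP wording, three all-subject tables and three figures, and the non-dexamethasone outputs that the text already promises. It uses existing data and needs no protocol amendment.

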3.2.2. Secondary Efficacy Endpoints

Secondary efficacy endpoints of this study are:

- Change and percent change from baseline in plasma or serum biomarkers: 17-OHP, ACTH, androstenedione (A4), and testosterone.

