4.3. Sample Size Considerations

The sample size of up to approximately 24 subjects in this study is based on an estimate of the number of subjects who may enroll either after completing Study SPR001-201 or as SPR001-naïve subjects. There is no statistical basis for the sample size,

The final sample size for the study is n=11.

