4.4. Randomization

This is an open label study. All enrolled subjects receive the same treatment with no randomization.

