5. PLANNED ANALYSES

5.1.1. Changes to Protocol Specified Analyses

Due to the low enrollment numbers for subjects enriched with acne and hirsutism at baseline (n=2), these endpoints will not be summarized.

Due to no samples collected, analysis of semen will not be summarized.

Due to the study short duration and lack of adequate baseline data, menstrual cyclicity will not be summarized.

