6.6.4. Visit Windows

All assessments will be summarized using analysis windows.

The terminology of unscheduled will be applied to assessments that are outside an analysis window regardless, of the nominal label associated with the assessments in the EDC system.

The following visit windows will be used in the summary of clinical data.

Table 3: Analysis Visit Windows

Nominal Period/Visit	Start (days)	Stop (days)
Baseline	1	1
Week 2 (Day 15)	2	21
Week 4 (Day 29)	22	35
Week 6 (Day 43)	36	49
Week 8 (Day 57)	50	63
Week 10 (Day 71)	64	77
Week 12 (Day 85)	78	91
Week 16 (Day 112)	92	120

Safety Endpoints

The following windows summarize the definition of treatment-emergent.

Table 4: Analysis Windows for Safety Endpoints

Window	Start	Stop
Adverse events	Sign of ICF	30 days post last dose
Treatment-emergent Adverse events, ECGs and Labs	Post first dose	Last dose + 30 days
Prior Medications	Prior to first dose	First dose
Concomitant Medications	Post first dose	Last dose + 24 hours
Post Medications	Post last dose + 24 hours	NA

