9.3. Subgroup Analyses

Subgroup analyses will characterize the consistency of the treatment effect across select subject subgroups. Subgroups analyses using the pre-specified subgroups in Section [6.4.5](#) will be repeated for select analyses as specified in subsequent SAP sections.

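### The hormone-control classes are cut on the same Day 1 ACTH and A4 values that serve as the change reference, and SAP 9.5 and the output index provide no unsplit by-visit summary of 17-OHP, ACTH or A4 to set beside them

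*SAP*

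**What the plan says.** **Class rule.** SAP 6.4.5 pre-defines the subgroup "Baseline hormone control: [a] severe/moderate control issues, [b] mild control issues". SAP 6.6.3 defines the upper class as "Severe/Moderate: Baseline ACTH > 2x ULN and A4 > 2x ULN" and Mild as both hormones at or below 2x ULN.

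**Change reference.** SAP 6.5 (Table 2) sets the biomarker baseline at Day 1 before dosing. SAP 6.6.4 says "All assessments will be summarized using analysis windows", and its Table 3 gives Baseline a window of Day 1 only. The endpoint in SAP 3.2.2 is "Change and percent change from baseline in plasma or serum biomarkers: 17-OHP, ACTH, androstenedione (A4), and testosterone", and SAP 9.2 compares baseline with Week 12.

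**Design.** SAP 4.4: "All enrolled subjects receive the same treatment with no randomization". SAP 4.3: "The final sample size for the study is n=11".

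**What is summarized.** SAP 9.5 restricts the hormone analysis to subgroups. For 17-OHP, ACTH and A4, the tables and figures in SAP 11.3 cover four sets each: Dexamethasone subjects, Non-Dexamethasone Severe/Moderate, the same with LOCF, and Non-Dexamethasone Mild. Testosterone alone has an all-subject table (14.2.4.1) and figure (15.2.4.1).

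**Stated purpose of the subgroups.** SAP 9.3: "Subgroup analyses will characterize the consistency of the treatment effect across select subject subgroups". SAP 9.5.2 repeats this aim for the hormone subgroups.

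**The concern.** One measurement does two jobs. A subject whose Day 1 ACTH or A4 happens to be high that morning is more likely to be put in Severe/Moderate, and the next value will on average be lower. The reverse holds in Mild. Without a control arm, nothing in the class tables separates this from a drug effect. The LOCF versions of the Severe/Moderate tables inherit the same problem.

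The usual protection is an estimate from subjects who were not selected on the reference value. The index offers none for these three hormones. The two class tables also omit any Non-Dexamethasone subject with one hormone above 2x ULN and the other not. At stake is the secondary efficacy readout. The fall in the more severe class may be overstated, and a difference between classes that SAP 9.3 would read as bearing on consistency would be partly artefact.

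**Working it through.** **1. The passages side by side.**

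| Place | Unsplit summary of 17-OHP, ACTH, A4? |
|---|---|
| Protocol 9.3.1 | Yes: data pooled over all subjects in each analysis population |
| SAP 9.5 | No: subgroups only |
| SAP 9.5.1 | Yes, as read: by-visit summary and figures for all four hormones, no split named |
| SAP 9.5.2 | Yes for Non-Dexamethasone: listed first, separately from its two control classes |
| SAP 11.3, tables 14.2.1.x to 14.2.3.x and figures 15.2.1.x to 15.2.3.x | No |
| SAP 5.1.1, "Changes to Protocol Specified Analyses" | Lists acne and hirsutism, semen and menstrual cyclicity; not this |

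**2. Who falls out.** From the ULNs in SAP 6.6.3, the cuts are ACTH 2 x 63.3 = 126.6 pg/mL, and A4 2 x 152 = 304 ng/dL (males) or 2 x 262 = 524 ng/dL (females). Both classes require the two hormones to agree. A Non-Dexamethasone subject above one cut only is in neither class, so for these hormones appears after baseline only in listing 16.2.6.1. The documents do not say whether any of the 11 is such a subject.

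**3. Direction and size.** There is no document figure to reproduce. The following are assumptions: no drug effect, between-subject log-SD s of 0.8 to 1.0, visit error variance e² = ln(1 + CV²), serial error correlation r, cut at the population median, and no entry rule. For one hormone classed on its own Day 1 value:

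expected log change above the cut = -(1 - r) x e² / √(s² + e²) x 0.798, with the opposite sign below it.

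- CV 50%, r = 0, s = 1.0: e² = ln 1.25 = 0.223, and 0.223 / 1.106 x 0.798 = 0.161. This is -15% above the cut and +17% below.
- CV 20%, r = 0.5, s = 0.8: e² = ln 1.04 = 0.0392, and 0.5 x 0.0392 / 0.824 x 0.798 = 0.019. This is -2% and +2%.

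The SAP rule uses two hormones jointly, so it was simulated with true correlation between hormones 0.5 to 0.7 and same-draw error correlation 0.5. ACTH, Severe/Moderate / Mild (A4 agrees within a point):

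| CV | Independent visit errors | Serial correlation 0.5 |
|---|---|---|
| 20% | -3 to -4% / +3 to +4% | about -2% / +2% |
| 30% | -7 to -9% / +7 to +9% | -3 to -5% / +3 to +5% |
| 50% | -15 to -19% / +18 to +24% | -8 to -10% / +9 to +11% |

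At CV 50%, moving the cut by 0.5 SD either way and the error correlation to 0.3 or 0.7, with or without a 17-OHP entry rule, gave -8 to -28% / +11 to +49% with independent errors. No sign changed. With no split the change was 0 for all three hormones.

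**4. 17-OHP.** It is not in the class rule. Correlation of true levels alone does not bias it. With same-draw error correlation set to 0 (s = 1.0, true correlation 0.5, CV 50%, independent visits), 17-OHP changes by about 0 in both classes, while ACTH in Severe/Moderate still shows about -12%. With error correlation 0.5, 17-OHP in Severe/Moderate shows -11 to -13% at CV 50%.

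**5. Precision.** 95% limits around no change are exp(± t × √2 × e / √n), with independent errors.

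- All 11, CV 50%: 2.228 x 1.414 x 0.472 / 3.317 = 0.449, so -36% to +57%. At CV 20%: -17% to +21%.
- An illustrative class of 4: -65% to +190% at CV 50%, and -36% to +56% at CV 20%.

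These intervals are wider than the artefact in step 3.

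**The case against.** **Much of the remedy is already in the SAP.** Sections 9.5.1 and 9.5.2 describe unsplit summaries, and 11.3 allows the index to be updated after finalization. A reader might infer that the sponsor has abandoned the pooled hormone summaries; the documents do not establish that. What remains is a contradiction. The restriction in 9.5 is body text, so updating the index alone does not resolve it.

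**The size is assumed and the stakes are modest.** This stands. Safety is the primary objective, SAP 9.4 calls the study hypothesis generating, and no test between classes is planned. SAP 9.1 provides nominal p-values. In a simulation assuming 5 subjects per class, a paired t-test at 0.05 rejected in 5.8% to 11% of cases with no drug effect (reliability 0.9 to 0.5). That does not support reading any significant fall as probably artefact. Still, a confidence interval shows imprecision and does not show a bias of known direction.

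**A reader might infer that every class table is biased.** The 17-OHP tables need correlated same-draw errors, about which the documents say nothing, so the directional claim covers ACTH and A4 only.

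**A reader might infer an undeclared change from protocol.** SAP 5.1.1 does not list it, but the text of 5.1.2 (revisions) was not in the copy read. Protocol 9.3.9 permits additional subgroups, though that does not replace the pooled summaries of 9.3.1.

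**Could the classes use the screening sample instead?** With independent errors that gives no bias in either class. For some rollover subjects, however, the screening value may come from the last SPR001-201 visit. It is an option, not a necessity, once the unsplit estimate is shown.

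**Conclusion.** The point holds for ACTH and A4. Classing on the values that are also the change reference, in a single arm, pushes Severe/Moderate towards a fall and Mild towards a rise. The direction needs only non-zero visit-to-visit variability. The size, about -2% / +2% (CV 20%, serial correlation 0.5) to -19% / +24% (CV 50%, independent errors), rests on the assumed log-SDs and correlations, a median cut and no entry rule. It is not an estimate for this trial, and at n=11 imprecision is larger. For 17-OHP the bias is conditional and may be nil.

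The conflict of SAP 9.5 and 11.3 with SAP 9.5.1, SAP 9.5.2 and protocol 9.3.1 needs no assumption, nor does the absence of a class for discordant subjects. These should be corrected. They do not invalidate the study or its safety conclusions.

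**What to change.** 1. Replace the restriction in SAP 9.5 with: *Hormone data will be summarized for all subjects, for all Non-Dexamethasone subjects, and then by subgroup.* In 11.3, ahead of the class tables, add the all-subject and the unsplit Non-Dexamethasone by-visit table and figure for 17-OHP, ACTH and A4. Discordant subjects are then included.
2. Keep the class tables and figures as descriptive. Footnote that the classes use the Day 1 ACTH and A4 values that are also the change reference, so regression to the mean is expected for those two hormones: a fall in Severe/Moderate and a rise in Mild. Amend 9.3 and 9.5.2 so that the contrast between control classes is not read as consistency of the treatment effect.
3. State that the unsplit estimate removes only the class-split bias. If visit errors are serially correlated, it may keep a small fall from the screening 17-OHP ≥800 ng/dL rule. With serial correlation 0.5 and an assumed 30% failing entry, this is -1 to -2% for ACTH and -3 to -5% for 17-OHP at CV 50%. That calculation applies the rule to everyone. The protocol applies it to all naïve subjects (5.2.1), but to rollover subjects only when screening is more than 3 months after SPR001-201 follow-up (5.1.1).
4. Show Week 16 values for context only. Protocol 4.2 allows for rebound and gives 32 to 44 days for essentially complete elimination, against 30 days of follow-up. The Table 3 window also ends at Day 120, whereas a last dose on Day 84 with follow-up at 30 + 7 days falls on Day 121.

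Cost: SAP wording, footnotes and six by-visit tables with figures (three hormones, two groupings) from data already collected. Conduct and sample size do not change.
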